6.6.2 Secondary endpoint

All secondary endpoint analyses will be performed for the FAS only, unless specifically stated that mFAS will also be used. All secondary endpoint analyses will be done on the overall treatment period, unless otherwise specified.

Free plasma oxalate

Change in free plasma oxalate level during OC5 treatment will be analyzed descriptively (tables and plots) as described for the primary endpoint.

Total and free plasma oxalate levels from week 10 to week 14

After 6 weeks of treatment, there is a 4 week off-treatment period scheduled. Change in total and free plasma oxalate levels following the 4 week off-treatment at week 12 and 14 will be calculated as the value at visit 12 or 14 minus the visit value at week 10. Summary statistics of the measurements will be presented on a per-visit basis. Both the actual value as well as the change from baseline value will be presented for the FAS. For handling missing data in summary statistics for CFB values, see section [6.2](#).

***O.formigenes* in faeces**

Data collected for *O.formigenes* in faeces will only have measurable values if above the Limit of Quantification (LOD). Values below the LOD will be replaced for calculation purposes in descriptive statistics, plots and statistical analyses (see section [9.1](#)). The proposed analyses will only be performed if there is a limited amount (<15%) of data below LOD present. The values will be presented as ‘< LOD’ in the listings. Note that in case of a provided value lower than the LOD, it will be presented and used as is and not imputed.

Change in the number of *O.formigenes* in faeces during OC5 treatment will be calculated at each visit as the visit value minus the baseline value. Summary statistics of the measurements will be presented on a per-visit basis. Both the actual value as well as the change from baseline value will be presented. Statistics will be presented for genotype 1, genotype 2 and the sum of both genotypes, only if there are enough data > LOD (to be checked separately for the treatment phase and the continued phase). If only for one of the genotypes this is the case, statistical presentations will just be performed on the data belonging to that specific genotype. Data for the other genotype will then be limited to a listing, and the sum for both genotypes will not be calculated.

To visualize the effects through time graphically, the following plots will be created. All faeces plots will be created for the overall treatment period as well as the continued treatment period (including baseline value) alone:

- Mean +/- SE and individual plots will be created for *O.formigenes* (genotype 1, genotype 2 and sum of both genotypes, when feasible) values through time. Only the actual values will be presented.
- Furthermore, the relationship between *O.formigenes* and total plasma oxalate over time will be evaluated graphically. These comprise of:

- Mean +/- SE and individual plots plotting the time course of genotype 1, genotype 2 and total plasma oxalate (when feasible) in one graph using double axes.
- Individual scatterplots and a combined scatterplot of faeces versus total plasma oxalate. Scatterplots will be created separately for the sum of both genotypes, genotype 1 and genotype 2 (when feasible). For these plots, only time points can be used when both assessments were made, where 'baseline' is considered the same time point even if assessed at different weeks.

If possible, a correlation analysis between *O.formigenes* and total plasma oxalate will be done as well. A repeated measures model can be used to determine the "repeated measures correlation" between total number of *O.formigenes*, or one of the genotypes with sufficient data, and total plasma oxalate. Note that the limiting factor here is the count data for *O.formigenes*: this type of data generally deviates from normality. Therefore, for this correlation analysis, the total number of *O.formigenes* may be log transformed by executing $\ln(O.formigenes)$ where \ln is the natural logarithm. If this transformation does not suffice, another transformation may be used, however it should be noted that it is possible that no transformation will suffice with the desired effect of reaching normality, therefore results should be considered with caution. The correlation coefficient will be presented in a table.

Speckle Tracking/Traditional Echocardiography

Change in Speckle Tracking/Traditional Echocardiography parameters, collected at screening and during continued treatment, will be calculated at each visit as the visit minus the baseline value.

Speckle Tracking Echocardiography (STE) parameters are Image Quality, Global Longitudinal Strain (GLS), Global Circumferential Strain (GCS), Rotational Displacement, Average Apical Longitudinal Strain, Average Mid Longitudinal Strain, Average Basal Longitudinal Strain and Relative Apical Longitudinal Strain (RALS; defined as Average Apical Longitudinal Strain / (Average Basal Longitudinal Strain + Average Mid Longitudinal Strain)).

Traditional Echocardiography (TE) parameters are Left Ventricular Ejection Fraction (LVEF), Left Ventricular Mass Index (LVMI), Left Ventricular End Diastolic (LVED) Dimension, Interventricular Septal (IS) Thickness at End-diastole, Pulse Wave doppler (PW) Thickness at End-diastole, e/é, e/a, Tricuspid Regurgitation and Continuous Wave Doppler.

Summary statistics of the parameters will be presented on a per-visit basis. For all parameters (except for Image Quality and Tricuspid Regurgitation), both the actual value as well as the change from baseline value will be presented. For Image Quality and Tricuspid Regurgitation, the number/percentage of observations in the different categories will be presented per visit. STE parameters and TE parameters will be presented in separate tables for the FAS and mFAS.

To visualize the effects through time graphically, the following plots will be created for FAS and mFAS, using the overall treatment period:

- Mean +/- SE and individual plots will be created for GLS/LVEF/RALS values through time. Presentations are made for the actual values and the CFB values.
- Combined spaghetti plots will be created using the actual values. No spaghetti plots will be created for change from baseline.
- Furthermore, the relationship between GLS/LVEF/RALS and total plasma oxalate/free plasma oxalate over time will be evaluated graphically. These comprise of:
 - Mean +/- SE and individual plots plotting the time course of GLS/LVEF/RALS and total plasma oxalate/free plasma oxalate in one graph using double axes.

- Individual scatterplots and a combined scatterplot of GLS/LVEF/RALS versus total plasma oxalate/free plasma oxalate. For these plots, only time points can be used when both assessments were made, where 'baseline' is considered the same time point even if assessed at different weeks.

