Faeces: The measurement at week 4 is considered the baseline value.

Echography: The screening value is used as baseline. If this value is missing, the CT week 0 value is used as baseline value instead.

Safety lab: Safety lab is determined at screening and at week 4. The week 4 measurement is considered the baseline value. If this value is missing, the screening value will be used instead.

Data for screening failures will not be presented in summary tables, except for disposition and end-of-study displays, provided end-of-study data includes screen failures. Data for screening failures will be listed as available.

For this study, a treatment emergent adverse event (TEAE) is defined as an adverse event reported on or after first dose of study treatment. AEs after last dose date, and thus also after study drop-out, are not collected.

All descriptive statistics tables will be presenting data per visit, if applicable.

Any statistical significance determined in the analyses will be viewed with caution, considering the very small and heterogeneous patient population. Any determined p-values can only be indicative. No correction for multiple comparisons will be applied for any of the endpoints.

All collected data will be presented as is in individual data listings, and no other (calculated) data will be added unless specifically specified in the respective section. In case derived variables are to be added to the listings, both the original variable as well as the derived will be presented. For all relevant listings, study day will be added. The calculation for this day is as described in section 9.1.

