9 TECHNICAL DETAILS

9.1 Programming conventions

In the database, the variable ETHNIC is collected. However, following SDTM, its contents are more in line with what should have been collected as RACE. Therefore, we convert this variable to race, and program ethnicity as UNKNOWN.

Due to a systematic error in molarity values reported, the values for total plasma oxalate need to be converted by multiplying the received values by a factor of 0.71. This will be done for all listings, tables and graphs displayed for the study.

O.formigenes (genotype 1, genotype 2 and sum of genotypes) counts will be reported in $\times 10^6$. Data collected for *O.formigenes* in faeces will only have measurable values if above the LOD. Values below the LOD will be reported as 0 in the dataset. These values will be replaced with $LOD/\sqrt{2}$ for calculation purposes in descriptive statistics, plots and statistical analyses, only when there is a limited amount of data $< LOD$ present. The LOD values used are 118.000 ($0,118 \times 10^6$) for genotype1 and 37.900 ($0,0379 \times 10^6$) for genotype2. Note that in case of a

provided value lower than the LOD, it will be presented and used as is and not replaced with the LOD value.

BMI will be calculated in SAS as follows: weight/height², with weight in kg and height in meter (unit kg/m²).

For STE and TE parameters, a value of -99 in the database indicates that the value is missing, and these values will be treated accordingly.

Relative Apical Longitudinal Strain (in STE data) will be added to the analysis. Relative Apical Longitudinal Strain (LS) is calculated as: RALS = Avg. apical LS / (Avg. basal LS + Avg. mid LS).

Durations, determination of baseline values and handling of missing data will be programmed as stated in the respective analysis sections.

Study day will be added to some of the listings and calculated as follows: if the study date is before the date of first study dosing, then study day = first dose date – collection date. If the study date is after first dosing, then study day = collection date – first dose date +1. Time will be no factor in the calculation. If the study date is (partly) missing, and study date is before first dose date, then the first day of the month, and/or the first month of the year will be used. If collection date is completely missing, then study day cannot be determined.

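### Faecal O. formigenes results below the limit are scored by two different rules (0 becomes LOD/√2, provided numbers stay as they are), which can give an unknown change a spurious sign

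*SAP*

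**What the plan says.** Change in faecal O. formigenes during treatment is a secondary endpoint (SAP 5.2). SAP 6.1 fixes the baseline: "Faeces: The measurement at week 4 is considered the baseline value". Under SAP 6.6.2, change "will be calculated at each visit as the visit value minus the baseline value", so the planned change is on the raw count scale.

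For low counts, SAP 9.1 gives a coding rule, "Values below the LOD will be reported as 0 in the dataset", and a substitution rule, "These values will be replaced with $LOD/\sqrt{2}$ for calculation purposes in descriptive statistics, plots and statistical analyses". It also gives the limits: "The LOD values used are 118.000 ($0,118 \times 10^6$) for genotype1 and 37.900 ($0,0379 \times 10^6$) for genotype2".

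The same section then makes an exception for any "provided value lower than the LOD, it will be presented and used as is and not replaced with the LOD value". SAP 6.6.2 states that exception too: "Note that in case of a provided value lower than the LOD, it will be presented and used as is and not imputed".

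The analyses are conditional: "The proposed analyses will only be performed if there is a limited amount (<15%) of data below LOD present". SAP 6.6.2 checks whether there are enough data separately for the treatment phase and the continued phase. It also plans, if possible, a repeated measures correlation with total plasma oxalate, for which the total count may be ln-transformed.

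**The concern.** Two rules cover the same stretch of the scale. One moves a sub-limit result up to LOD/√2; the other leaves it where it was reported. When both kinds of result occur in one patient or one scatterplot, their order is set by the coding and not by the bacteria.

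The SAP is also unclear about what the limit is. SAP 6.6.2 spells LOD out as a quantification limit, while the abbreviation list spells it out as a detection limit. Both 6.6.2 and 9.1 say that counts are measurable only above the limit, which sits badly with a rule for using numbers below it.

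At stake are the per-visit changes from baseline, the plots, and the correlation with total oxalate. Protocol 10.2 describes this measurement as an important pharmacodynamic check on the drug.

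**Working it through.** **Inputs.** LOD is 118,000 (genotype 1) and 37,900 (genotype 2), and the substitute is LOD/√2 (SAP 9.1). Change is visit minus week 4 (SAP 6.1 and 6.6.2). The 15% condition is in SAP 6.6.2. Initial-phase faecal samples are taken at weeks 4, 10 and 14 (Protocol 6.1). The provided values v used below are assumptions, because the documents give no sub-limit counts. The SAP states no figure on this point to reproduce.

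**Substituted values.**
- Genotype 1: 118,000/√2 = 83,439
- Genotype 2: 37,900/√2 = 26,799
- Both coded 0: 83,439 + 26,799 = 110,238 for the sum

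**Where the order is artificial.** A provided v scores below a sample coded 0 whenever v < LOD/√2. That is 1/√2 = 0.71 of the range from 0 to LOD for each genotype.

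**Raw change, genotype 1, from coded 0 to v** (v − 83,439):

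| Assumed v | Scored change |
|---|---|
| 11,800 (10% of LOD) | −71,639 |
| 50,000 | −33,439 |
| 59,000 (50%) | −24,439 |
| 106,200 (90%) | +22,761 |

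For v = 50,000 the coded 0 could stand for anything from 0 to 118,000. The true change therefore lies between 50,000 − 118,000 = −68,000 and +50,000. The data do not fix the sign, but the rule does.

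For genotype 2 with v = 15,000, the scored change is 15,000 − 26,799 = −11,799.

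**Bound on the raw error.** A substituted 0 overstates the count by at most LOD/√2 and understates it by at most LOD − LOD/√2.
- Genotype 1: 83,439 and 34,561
- Genotype 2: 26,799 and 11,101

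The larger of each pair gives 0.083 × 10^6 and 0.027 × 10^6 per sample.

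**Optional ln scale.** This is the difference in ln score between a sample coded 0 and a provided genotype 1 value:
- v = 50,000, genotype 1 alone: ln(50,000/83,439) = −0.51
- v = 10,000, genotype 1 alone: ln(10,000/83,439) = −2.12
- v = 50,000, total count, genotype 2 coded 0 in both samples: ln(76,799/110,238) = −0.36
- v = 10,000, total count, genotype 2 coded 0 in both samples: ln(36,799/110,238) = −1.10

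**How many samples the 15% condition lets through, initial phase** (three samples per patient):
- 6 patients: 2 of 18 (11.1%)
- 8 patients: 3 of 24 (12.5%)
- 12 patients: 5 of 36 (13.9%)

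If every week 4 sample were below the limit, the share would be at least 1/3 = 33% and the initial-phase analysis would not run.

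**Continued phase.** Protocol 11.5.1.2 reports eight patients continuing. Assuming all gave 8-weekly samples to week 104 (13 each, 104 in total), up to 15 (14.4%) could be below the limit. Fewer samples would lower that number.

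**Under one rule.** If every sub-limit result is set to LOD/√2, a change between two such samples is 0. A change across the limit keeps its correct sign, because any value at or above LOD exceeds LOD/√2.

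**The case against.** The tempting stronger reading is that a patient who goes from no bacteria to detectable bacteria is scored as having lost bacteria. The documents do not support that. In SAP 9.1 a 0 is a code for any result below the limit, not a measured absence. Going from that code to 50,000 could be a rise, a fall or no change. What stands is that the plan assigns a sign where none is known.

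A reader might also assume that pre-dose and off-drug samples sit at the low end, so that the problem is widespread. No document gives faecal counts for this trial, and Protocol 4.2 describes the organism as part of the normal gut flora. If most week 4 samples were below the limit, the 15% condition would stop the initial-phase analysis. It limits the number of affected samples but does not remove the problem.

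Four further objections carry weight:
- The exception appears in two places but is one rule repeated. It does not show that sub-limit numbers were ever supplied.
- No ln-scale change from baseline is planned. The ln transform is optional and belongs to a correlation done only if possible. The −2.12 applies only if genotype 1 is analysed alone.
- SAP 6.1 makes all evaluations exploratory, and the listings let a reader see which samples are affected.
- The single-rule fix does not recover a true rise below the limit; it scores it as zero. Leaving coded zeros at 0 would also restore the order and keep the provided numbers, but only in untransformed analyses, since ln(0) is undefined.

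These objections reduce the size and certainty of the point. None of them removes the overlap between the two rules, and no other part of the SAP resolves it.

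**Conclusion.** The inconsistency is real and follows from the SAP's own text. Provided values in the lower 71% of the sub-limit range are scored below samples coded 0, so a change or ranking between two sub-limit samples can carry a spurious sign. Comparisons with samples above the limit keep the right direction.

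On the raw scale, where the secondary endpoint is calculated, the effect is small if on-treatment counts lie well above the limit; the documents do not say whether they do. On the optional ln scale a single sample could matter more in a trial of 6 to 12 patients. The conclusion depends on two conditions: fewer than 15% of data are below the limit, and at least one number below LOD/√2 is supplied. Severity is minor.

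**What to change.** In SAP 6.6.2 and 9.1:

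1. State whether LOD is a detection or a quantification limit, and that 0 is the code for a result below it.
2. For descriptive statistics, plots and analyses, set every result below the genotype's limit to LOD/√2, whether it arrives as 0 or as a number. Remove the two exceptions for calculations.
3. Say that all such results count toward the 15% limit. The present wording probably means this but does not say it of provided numbers.
4. Keep received values in the listings.

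This costs two sentences and one programming condition. The downside is that imprecise sub-limit numbers drop out of the summaries and any change between two sub-limit samples scores as zero. That is in keeping with the SAP's own statement that counts are measurable only above the limit.

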10.3 Speckle Tracking Echocardiography and Traditional Echocardiography

Speckle Tracking Echocardiography is currently evaluated as a method to detect and quantify oxalate deposits in the heart muscle.¹³ Speckle Tracking Echocardiography and traditional echocardiography will be performed at screening (alternatively before start of continued treatment) and repeated every 6 months during the continued treatment period, if possible. The examination will be performed locally using specific equipment. Images will be interpreted by a central reader who is blinded to plasma oxalate and examination date.

Speckle Tracking Echocardiography results will be evaluated for changes in Global Longitudinal Strain, including segmental changes, Short-Axis Myocardial Function, Rotational Displacement and Apical Sparing Patterns. Traditional echocardiographic parameters will also be evaluated (Ejection Fraction, End Diastolic Volume, e/é, e/a, Left Ventricular End Diastolic Dimension, Fractional Shortening, Tricuspid Regurgitation by Doppler as an indicator of RV/pulmonary pressure). A positive treatment effect would be an improved myocardial function based on the above-mentioned parameters, decreased Global Longitudinal Strain, improved Rotational Displacement and reduced/removed Apical Sparing Pattern. The treatment effect on STE parameters will be compared to traditional echocardiography parameters of LV and RV function to determine which assessment of cardiac function is more sensitive in these patients.

Speckle Tracking Echocardiography examinations performed during the study, but before this amendment's effective date will be re-evaluated to retrospectively capture the above-mentioned parameters to be included in the statistical analysis.

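### SAP 6.6.2 leaves two of the protocol's seven traditional echo parameters out of the summaries and adds three or four others, and SAP section 7 records none of this

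*SAP*

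**What the plan says.** **Protocol 10.3** gives the traditional list as "Ejection Fraction, End Diastolic Volume, e/é, e/a, Left Ventricular End Diastolic Dimension, Fractional Shortening, Tricuspid Regurgitation by Doppler". That is seven parameters, introduced by "Traditional echocardiographic parameters will also be evaluated (Ejection Fraction, End Diastolic Volume". The section describes a positive effect as better myocardial function on the parameters it has just listed, and it plans to compare speckle tracking with traditional measures of left and right ventricular function for sensitivity. For examinations done before the amendment took effect, it says they "will be re-evaluated to retrospectively capture the above-mentioned parameters to be included in the statistical analysis".

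**SAP 6.6.2** (Speckle Tracking/Traditional Echocardiography) lists "Traditional Echocardiography (TE) parameters are Left Ventricular Ejection Fraction (LVEF), Left Ventricular Mass Index (LVMI), Left Ventricular End Diastolic (LVED) Dimension" and then "Interventricular Septal (IS) Thickness at End-diastole, Pulse Wave doppler (PW) Thickness at End-diastole, e/é, e/a, Tricuspid Regurgitation and Continuous Wave Doppler". That is nine parameters, worded as the complete set. All except tricuspid regurgitation, which is categorical, are to be summarised as value and change from baseline. Table 14.2.30 is the corresponding output, for FAS and mFAS.

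**SAP section 1** says the plan agrees with protocol version 12, which contains the list in 10.3.

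**SAP section 7**, the place for changes to the protocol, records two echo items. One is the addition of Relative Apical Longitudinal Strain, first called Apical Sparing Patterns. The other is the removal of the global radial and global circumferential peak systolic strain measures. Both concern speckle tracking.

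**The concern.** A reader who goes to SAP section 7 to learn how the analysis departs from the protocol finds echo changes itemised there. That reader would reasonably conclude that the rest of the echo set follows the protocol. For the traditional parameters it does not.

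The choice of parameters carries weight here because nothing else constrains the echo conclusion. SAP 6.1 plans no formal testing and no correction for multiple comparisons. SAP 2.4 bases inference on clinical relevance. Protocol 11.5.1.2 reports 12 treated patients, of whom eight entered continued treatment. With data like these, the parameters shown in the summary table largely determine what the report says about traditional echo.

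This SAP version was also written after echo results had been seen. Section 7 describes the first interim in the past tense, SAP 6.3 gives cardiac function as one of the two interim aims, and Protocol Table 3 already reports interim signs of improved myocardial function. The risk is selective reporting of a descriptive secondary endpoint, or the appearance of it. Type I error is not at stake.

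**Working it through.** No sample size, power or error rate bears on this point. The check is a comparison of the two lists, followed by a search of SAP section 7 for each difference.

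| Parameter | Protocol 10.3 | SAP 6.6.2 | Recorded in SAP section 7 |
|---|---|---|---|
| Ejection fraction | yes | yes | not needed |
| LV end diastolic dimension | yes | yes | not needed |
| e/é | yes | yes | not needed |
| e/a | yes | yes | not needed |
| Tricuspid regurgitation | yes | yes | not needed |
| End Diastolic Volume | yes | no | no |
| Fractional Shortening | yes | no | no |
| LV mass index | no | yes | no |
| Septal thickness at end-diastole | no | yes | no |
| PW thickness at end-diastole | no | yes | no |
| Continuous Wave Doppler | not by name | yes | no |

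**Counts**
- Protocol 7, SAP 9, shared 5.
- Omitted: 7 − 5 = 2, so 2 of 7.
- Added: 9 − 5 = 4. If Continuous Wave Doppler is the measurement behind the protocol's tricuspid regurgitation item, the SAP has 8 distinct items and the additions are 8 − 5 = 3.
- Differences recorded in section 7: 0 of 6 (2 + 4), or 0 of 5 (2 + 3).

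**Is the protocol list a commitment?** The opening of the list says the parameters will be evaluated. The later sentence on re-evaluation sends the listed parameters into the statistical analysis. That sentence is worded for speckle tracking examinations, but it comes after both lists and refers back to them, and the summary of Amendment XI names both kinds of examination. A plan to analyse the traditional list is the natural reading.

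**When did the lists diverge?** Nothing dates the traditional list. SAP section 1 required a signed SAP before the first interim, and earlier SAP versions are not available. The version at hand is later than that interim, but the difference in lists could be older.

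**Label.** The item "Pulse Wave doppler (PW) Thickness at End-diastole" joins a Doppler mode to a wall-thickness quantity, so the variable cannot be identified from the text.

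**The case against.** The strongest reply is that this is a gap in documentation and nothing more. Several parts of that reply stand.

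- **Timing.** A reader might infer that the outcome set was changed after the interim results were known. The documents do not support that. Section 7 lists several differences between the first interim and the final analysis and names no traditional parameter among them. This fits at least as well with a list unchanged since before the interim.
- **Suppression.** A reader might also infer that the two parameters will not be reported at all. SAP 6.1 says all collected data go into individual listings, and listing 16.2.6.4 covers traditional echocardiography. If the values were collected, they will appear per patient, and only the summaries are missing. The SAP was written against a blank CRF dated 16 October 2019, which is not available here, so the two parameters may simply not be on it.
- **Number of additions.** The protocol asks for tricuspid regurgitation by Doppler as an indicator of right ventricular and pulmonary pressure. The SAP's categorical regurgitation item and its Continuous Wave Doppler item may together carry that out. Four additions is therefore an upper count.
- **Protections.** Images are read centrally by a reader blinded to plasma oxalate and examination date. The echo plots use only global longitudinal strain, ejection fraction and relative apical longitudinal strain, so no added parameter is plotted. The explicit signs of benefit in Protocol 10.3 are speckle tracking measures. The endpoint itself fixes no traditional list, and Protocol 12.1 leaves further definition to the SAP.

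These points limit the concern but do not remove it. Blinded reading guards against biased measurement and does nothing about which measurements are summarised. Leaving detail to the SAP does not cover dropping two named parameters without a record in a document that states agreement with the protocol.

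**Conclusion.** The point holds as a minor one. Two of the seven traditional parameters in the protocol are missing from the planned summaries, three or four others are added, and SAP section 7 records none of these five or six differences. The SAP's statement of agreement with protocol version 12 is therefore not accurate for this endpoint.

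The conclusion rests on reading the SAP list as complete, which its wording supports, and on treating the protocol list as what was to be analysed. It does not depend on when the lists diverged. The stronger claim, that parameters were chosen in the light of interim results, is not established: no document dates the traditional list, and the interim statement about myocardial function cannot be tied to any added or omitted parameter. What can be said is that an unrecorded departure stands in a SAP version that postdates the first interim, and the sponsor can clear this up from its own records.

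**What to change.** 1. Add End Diastolic Volume and Fractional Shortening, as value and change from baseline, to SAP 6.6.2 and table 14.2.30. If they are not in the database, say so in section 7 with the date and reason, as is already done for the removed strain measures.
2. Record each added traditional parameter in section 7, with its date relative to the first interim. Label as post hoc only those added after it. State whether Continuous Wave Doppler is a separate parameter or the measurement of tricuspid regurgitation.
3. While editing the list, correct the PW label to the quantity actually measured.

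If the data exist, the cost is two extra rows in one table (shown for FAS and mFAS) and a short paragraph in section 7. If they do not, it is wording only. No change to design, consent or data collection is needed.
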